This study is being conducted to address a Food and Drug Administration (FDA) postmarketing requirement to conduct a single-arm prospective and retrospective observational study of pregnant women exposed to Repatha to evaluate fetal and infant outcomes through the first year of life. This study will estimate the proportion of pregnancy and maternal complications, adverse events in the developing fetus and neonate, and adverse events in the infant through the first year of life using data from pre-existing reports within Amgen's Global Safety Database.

- Research Question and Objective(s)

Objectives	Endpoints
Primary	
Among women exposed to Repatha during pregnancy, to estimate the proportion of: 
- Pregnancy and maternal complications- Adverse events in the developing fetus and neonate- And among their infants, adverse events for the first year of life.	
• Number of cases reporting pregnancy and maternal complications.• Pregnancy Outcomes: Number of cases reporting live full-term births, spontaneous abortion, elective abortion, stillbirth, and premature delivery.• Infant Outcomes: Number of cases reporting adverse events including complications, medical problems or congenital anomalies at birth.• Number of cases reporting adverse events at 6 months and 12 months.

- Hypothesis(es)/Estimation

This is an estimation study. No formal hypothesis will be tested.

- Study Design/Type

This is a Global prospective and retrospective observational case series of pregnant women exposed to Repatha during pregnancy and their infants through the first year of life.

- Study Population or Data Resource

Case finding through the Amgen Global Safety Database and other post marketing sources which include: spontaneous (including regulatory authority and literature), solicited (ie, patient support programs and market research), and postmarketing non-interventional studies. Retrospectively, data will be extracted from pre-existing postmarketing reports obtained from Amgen's Global Safety Database for women exposed to Repatha during pregnancy and their infants between July 2015 and the approval date of this protocol. Prospectively, from approval date of this protocol through July 2025, secondary data from postmarketing reports will be analyzed for women who have been exposed to Repatha during their pregnancy and their infants. Patients who refused consent will be excluded.

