8.4 Data Sources

The Amgen Global Safety Database is a comprehensive pharmacovigilance database that contains reports of adverse event data for all Amgen products including Repatha and all safety reports from clinical and post market sources. Amgen performs follow-up on adverse events reported for all products including Repatha as per Amgen's due diligence process. The Amgen Global Safety Database includes reports of pregnancy, birth outcome, and infant health information of women who have had direct exposure to Repatha prior to or during pregnancy. Pregnant women may or may not provide consent for their health and their children's health information to be obtained by Amgen. The database contains positive and negative pregnancy outcome data, including congenital

anomalies, spontaneous and elective abortions, fetal death/stillbirths, and premature birth.

All Repatha pregnancy cases (which may include multiple pregnancies from the same woman), of which Amgen becomes aware, reported from the postmarketing experience (including through spontaneous reporting, cases solicited through patient support programs, market research, from the literature, from regulatory authorities, or postmarketing non-interventional studies) are entered into the Amgen Global Safety Database. Pregnancy exposure case reporting and follow-up through the infant's first year of life is voluntary and participants are free to withdraw at any time.

Amgen does not provide compensation for participation in the follow-up process. Participants are required to provide verbal or written consent that allows Amgen to collect relevant pregnancy, birth outcome, and infant health information.

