As per Amgen's due diligence process, upon notification of a Repatha exposure during pregnancy (with or without an adverse event), Amgen Global Patient Safety follows up with the reporter to request informed consent to obtain pregnancy and infant health information from the mother. Follow-up will be performed as per Amgen's routine pharmacovigilance process at predefined intervals and adjusted accordingly depending on whether the mother is pregnant or has already delivered. Information requested may include, but is not limited to, alternate contact information for the mother, such as contact information of a close relative or friend, pregnancy/delivery details, medical history, laboratory and diagnostic tests, and HCP names. The process includes a set number of follow-up attempts over predefined intervals (post birth, when the infant is 6 months and 12 months). If there is no response to the follow-up attempts the due diligence process is complete and the case is considered lost to follow-up. An exception to this process is when the reporter explicitly states they are not prepared to provide any further information, did not provide consent to follow-up, or refused to provide any additional information about the pregnancy or infant. If this occurs, follow-up is not conducted.

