8.7.2.3.3 Analysis of the Primary, Secondary, and Exploratory Endpoint(s)

All analyses will be descriptive. These cases constitute a case series, thus line listings of pregnancy and maternal complications, pregnancy outcomes, infant outcomes and adverse events will be summarized along with tabulations of the numbers and frequencies of events by category of report: numbers who did not provide consent for follow-up, timing of exposure (first, second, or third trimester), and indication for use of the medication. Collection of exposure and outcome information in this group provides additional evidence on the safety of Repatha use during pregnancy. The denominator is the number of pregnant women exposed to Repatha during pregnancy and the numerator is the number with the outcome.

The proportion of infants with adverse events including complications, medical problems or congenital anomalies at birth will be assessed in infants of women exposed to Repatha during pregnancy with corresponding 95% confidence intervals. The proportion of infants with adverse events at 6 months and 12 months of age will be assessed. All adverse events among mothers who have received Repatha at any time during the pregnancy will be summarized including the proportion with pregnancy and maternal complications. To assess events in the developing fetus and neonate in women exposed to Repatha during pregnancy, the proportion of pregnancies resulting in spontaneous abortions, elective abortions, fetal death/ stillbirths and premature delivery will be presented, along with corresponding 95% confidence.

If the available safety information relevant to exposure during pregnancy represents a safety signal, the signal will be further evaluated through the Amgen safety governance structure and, if deemed necessary, escalated for consideration of changes to the Reference Safety Information (eg, USPI) as well as other forms of risk communication (eg, Dear Healthcare Provider Letters).

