8.7.5 Limitations of the Research Methods

8.7.5.1 Internal Validity of Study Design

8.7.5.1.1 Measurement Error(s)/Misclassification(s)

Identification of pregnant women exposed to Repatha depends upon the accuracy of the incoming information received by Amgen's Global Safety Database. Amgen has a comprehensive system to detect these events and a process to verify the data. However, the postmarket data may have missing information which could lead to not classifying the report as a pregnancy case.

Misclassification of outcomes due to poor patient recall should be reduced in this retrospective and prospective study design. For those women exposed to Repatha during pregnancy that are identified retrospectively, they are likely to accurately recall any maternal complications, pregnancy outcomes, adverse infant outcomes and events that may have occurred. However, exposed pregnant women that do not experience complications or adverse events may be less likely to consent to follow-up or may be lost to follow-up which would affect the denominators for aggregate outcomes.

A limitation of the study design relates to the evaluation of spontaneous abortion rates. Rates of early spontaneous abortion, ie, at 7 to 9 weeks post-LMP or less, will not be measured in a study that enrolls women after recognition of pregnancy. The study results with respect to spontaneous abortion will be limited to cases of late first-trimester and early second-trimester pregnancy loss.

Also, the calculation of frequency of birth defects excludes fetal losses (spontaneous abortions, elective abortions, or fetal deaths) for which no birth defects have been

detected. This may introduce a misclassification bias as there is no uniform evaluation of embryos or fetuses that do not survive. It is unknown what percentage of these pregnancies consists of potentially normal outcomes or structural defects. Amgen Global Safety will attempt to obtain information on structural defects detected at the time of the outcome. However, the malformation status of the aborted fetus may not be known. Therefore, defects reported in these groups will be considered separately from the primary analysis.

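### The one stated denominator, exposed pregnant women, conflicts with the infant and pregnancy proportions and the birth-defect rule; read literally it treats unknown outcomes as non-events

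*Protocol*

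**What the plan says.** The only explicit denominator rule is in Protocol Section 8.7.2.3.3 and, word for word, in the Data Analysis part of the abstract (Section 4): "The denominator is the number of pregnant women exposed to Repatha during pregnancy and the numerator is the number with the outcome". It carries no restriction to known outcomes, live births, or infants with 6- or 12-month information.

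Other text uses different bases:

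- **Infant events at birth** (next paragraph of 8.7.2.3.3): the proportion "will be assessed in infants of women exposed to Repatha during pregnancy with corresponding 95% confidence intervals".
- **Later infant events** (same paragraph): "The proportion of infants with adverse events at 6 months and 12 months of age will be assessed".
- **Pregnancy outcomes** (same paragraph): "the proportion of pregnancies resulting in spontaneous abortions, elective abortions, fetal death/ stillbirths and premature delivery will be presented".
- **Birth defects** (8.7.5.1.1): "the calculation of frequency of birth defects excludes fetal losses" in which no defect was found. Defects that are reported in losses are handled apart from the primary analysis. The same section says that non-consent and loss to follow-up would alter the denominators.

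Section 8.4 expects incomplete cases: "If there is no response to the follow-up attempts the due diligence process is complete and the case is considered lost to follow-up". It also shows that women and pregnancies are different counts: "All Repatha pregnancy cases (which may include multiple pregnancies from the same woman"). The questionnaires in Appendices C and D allow for multiple births. Section 8.7.2.2 says that missing data cannot cause bias because no association is assessed, then names overestimation through selective reporting as a possibility. Section 8.7.2.4 plans no sensitivity analysis.

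**The concern.** The deliverable of this FDA-required study is a set of proportions with 95% confidence intervals. A proportion means little until it is clear who is in its denominator, and here the text supports more than one answer for the same outcome.

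The literal rule is also the least suitable. A woman whose pregnancy outcome is never learned is counted below the line but can never appear above it. A pregnancy that ended in miscarriage is counted below the line for events at 12 months of age, which it cannot contribute. Annual interim reports (Section 8.7.1.1) add ongoing pregnancies and infants not yet 6 or 12 months old. In a safety study a diluted proportion reads as reassurance. If different annual reports adopt different readings, they will not be comparable.

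**Working it through.** The protocol gives no sample size, event rate or follow-up rate, so there is no figure to reproduce. All inputs below are assumptions chosen to show size and direction.

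**1. Dilution under the literal rule.** Let p be the event proportion among reported cases, f1 the share of event cases whose outcome becomes known, and f0 the same share for non-event cases.

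- Literal denominator: reported proportion = p × f1.
- Known-outcome denominator: reported proportion = p × f1 / (p × f1 + (1 − p) × f0).

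With f1 = f0, the known-outcome version returns p. The literal version gives:

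| p | 90% known | 70% known | 50% known |
|---|---|---|---|
| 3% | 2.7% | 2.1% | 1.5% |
| 10% | 9% | 7% | 5% |

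Since f1 cannot exceed 1, p × f1 never exceeds p. Relative to the reported cases, the literal rule can only lower the proportion.

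**2. Three readings of one 12-month proportion.** Assume 200 women, 120 live births (singletons), 84 infants with 12-month information and 21 with an event. Intervals are Clopper-Pearson.

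| Denominator | Proportion | 95% CI | Width (points) |
|---|---|---|---|
| 200 exposed women (literal rule) | 21/200 = 10.5% | 6.6 to 15.6% | 9.0 |
| 120 live-born infants | 21/120 = 17.5% | 11.2 to 25.5% | 14.3 |
| 84 infants with 12-month data | 21/84 = 25.0% | 16.2 to 35.6% | 19.4 |

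The first row follows the general rule. The second and third are both possible meanings of a proportion of infants. The interval narrows down to 9.0 points only because it counts people in whom nothing was observed.

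**3. Cases too recent to have 12-month data.** Assume 280 days from LMP to birth and LMP dates spread evenly over the 120 months from July 2015 to July 2025. Then 280 + 365 = 645 days, and 645 / 30.4375 = 21.2 months. So 21.2 / 120 = 17.7%, about 18% of pregnancies, could not have 12-month data by the end, yet would stay in the literal denominator.

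**4. Direction against all exposed pregnancies.** Suppose the true proportion is 10% and event pregnancies are twice as likely to be reported. The proportion among reported cases is 0.10 × 2 / (0.10 × 2 + 0.90) = 18.2%. Multiplying by 0.9, 0.7 and 0.5 gives 16.4%, 12.7% and 9.1% under the literal rule, on both sides of 10%.

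**5. The known-outcome denominator is not bias-free.** With p = 10%, f1 = 0.9 and f0 = 0.5, it gives 0.09 / (0.09 + 0.45) = 16.7%; the literal rule gives 9.0%. With f1 = 0.5 and f0 = 0.9, it gives 0.05 / (0.05 + 0.81) = 5.8%; the literal rule gives 5.0%. Missing outcomes can therefore bias a single-arm proportion in either direction, contrary to the opening claim of Section 8.7.2.2.

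**The case against.** The strongest defence is that the general sentence is loose drafting and the specific text governs: infants are the base for infant outcomes, pregnancies for pregnancy outcomes, and birth defects have their own rule. This stands in part. A reader might infer that the protocol divides every outcome by all exposed women, but the documents do not support that. Nor does any passage say that a case with unknown outcome counts as event-free. That follows only from applying the sentence literally, and Section 8.7.5.1.1, where loss changes the denominators, points the other way. Yet the specific text does not settle the matter: it never says whether infants without birth, 6-month or 12-month information stay in.

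A reader might also infer that the study's proportions are biased low overall. Sections 8.7.2.2 and 8.7.5.1.1 describe an opposing bias, since women without events may be less likely to report, consent or remain, and the net direction cannot be fixed from the documents.

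A third tempting reading is that the consent rules contradict each other, because the abstract says "Patients who refused consent will be excluded" while Section 8.2.2.2 lists no exclusions. Consent is an inclusion criterion in Section 8.2.2.1, so the two are compatible, and the tabulated number without consent can be read as an attrition count.

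Finally, premature delivery per pregnancy is a legitimate quantity that the protocol states, and interval methods for siblings or repeat pregnancies may be left to the SAP. Neither is part of this point. The denominator itself is different: the protocol states it, so an SAP must either follow it or contradict it.

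**Conclusion.** The point holds as an internal contradiction with a badly fixed general rule. What is certain is limited: read literally, the rule lowers each proportion relative to reported cases with known outcome, by the factor f1, and gives an interval that is too narrow for the information observed. How far depends on follow-up, which the protocol does not quantify. At assumed known shares of 90% down to 50%, the loss is a tenth to a half of the proportion. The 10.5% to 25.0% spread in the worked example rests wholly on assumed counts, and its lower end on the most extreme reading. It shows that the choice of denominator matters and does not forecast the study's results. No net direction of bias against all exposed pregnancies can be claimed. The statement in Section 8.7.2.2 that missing data cannot cause bias is wrong for estimated proportions, and sits badly with the overestimation that the same section acknowledges.

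**What to change.** Replace the general sentence in Section 8.7.2.3.3 and in the abstract with outcome-specific denominators:

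- **Spontaneous abortion, elective abortion, stillbirth:** pregnancies with known outcome.
- **Premature delivery:** pregnancies with known outcome, keeping the per-pregnancy base already stated; optionally also among live births.
- **Events and anomalies at birth:** live-born infants with birth information, with defects found in fetal losses reported separately as Section 8.7.5.1.1 provides.
- **Events at 6 and 12 months:** live-born infants with the corresponding report.

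Beside each proportion, show the number unknown, ongoing or lost, so that readers can judge a known-outcome proportion that may itself be biased upward. In Section 8.7.2.2, replace the claim of no bias with a statement that missing outcomes can bias the proportions in either direction.

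The cost is protocol wording, which under Section 11.1 goes to the FDA as an amendment, and matching table layouts. No new data are needed. Compared with the literal rule, some proportions will rise and intervals will widen.

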These cases constitute an exposed case series, thus line listings of pregnancy and maternal complications, pregnancy outcomes, infant outcomes and adverse events will be summarized along with tabulations of the numbers and frequencies of events by category of report: numbers who did not provide consent for follow-up, timing of exposure (pre-LMP, which trimester), and indication for use of the medication.

Collection of exposure and outcome information in this group provides additional evidence on the safety of Repatha use during pregnancy. The denominator is the number of pregnant women exposed to Repatha during pregnancy and the numerator is the number with the outcome. The proportion at birth with adverse events including complications, medical problems or congenital anomalies will be estimated in infants of women exposed to Repatha during pregnancy. The proportion of infants with adverse events observed at 6 months and 12 months of age will be estimated. The proportion of mothers who have received Repatha at any time during the pregnancy with pregnancy and maternal complications and adverse events will be summarized. Corresponding 95% confidence intervals will also be presented.

To assess effects on the developing fetus and neonate in women exposed to Repatha during pregnancy, the proportion with spontaneous abortions, elective abortions, fetal deaths/stillbirths and premature delivery will be presented, along with corresponding 95% confidence intervals

If the available safety information relevant to exposure during pregnancy represents a safety signal, the signal will be further evaluated through the Amgen safety governance structure and, if deemed necessary, escalated for consideration of changes to the Reference Safety Information (eg, United States Prescribing Information [USPI]) as well as other forms of risk communication (eg, Dear Healthcare Provider Letters).

5. Amendments and Updates

None.

6. Rationale and Background

In the United States (US), Repatha is indicated: (1) In adults with established cardiovascular disease to reduce the risk of MI, stroke, and coronary revascularization; (2) As an adjunct to diet, alone or in combination with other lipid-lowering therapies (eg, statins, ezetimibe), for the treatment of adults with primary hyperlipidemia (including HeFH) to reduce LDL-C; and (3) as an adjunct to diet and other LDL-C-lowering

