8.3.2 Outcome Assessment

Pregnancy outcomes include the number of women reporting pregnancy or maternal complications, as well as, the number reporting:

- Live full-term births
- Spontaneous abortion defined as non-deliberate fetal death which occurs prior to 20 completed weeks post-LMP
- Elective abortion defined as deliberate termination of pregnancy at any time in gestation
- Fetal death/Stillbirth defined as non-deliberate fetal death anytime in gestation at or after 20 completed weeks post-LMP
- Premature delivery defined as live birth prior to 37 weeks gestation as counted from LMP (eg, ultrasound adjusted date or Ballard's score)

Outcomes related to pregnancy and maternal complications will be assessed with a Pregnancy Questionnaire (a sample form included in [Appendix C](#)). Outcomes for live births will be assessed with a Post Due Date Questionnaire (a sample form included in [Appendix D](#)) from the Amgen Global Safety Database.

The number of infants with adverse events including complications, medical problems or congenital anomalies at birth will be assessed with a Post Due Date Questionnaire (a sample form included in [Appendix D](#)) from the Amgen Global Safety Database.

Major malformations or birth defects are defined as abnormalities incompatible with life or requiring medical/ surgical intervention. The term minor birth defect generally refers to minor physical anomalies with less clinical importance that represent deviations from what is considered normal and do not have obvious medical, surgical, or cosmetic consequences. Major birth defects identified up to 1 year of age by the mother or the healthcare provider will be included in the primary analysis. Major structural birth defects may be reported by the mother, a family member or her or her child's HCP via medical records. If a major malformation is reported the medical record will be adjudicated by a physician with expertise in teratology, pediatrics, and dysmorphology. Defects will be

classified using the Center for Disease Controls (CDC) criteria (CDC 2017.:
<https://www.cdc.gov/ncbddd/birthdefects/macdp.html>).

Infant outcomes are the number of cases reporting adverse events at 6 months and 12 months and may include whether they have not followed growth curves or met development milestones as expected for chronological age. These outcomes will be assessed with an Infant Questionnaire (a sample form included in [Appendix E](#)).

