Appendix E. 6- and 12-month Infant Questionnaire

Mother Safety Database #	
Infant Safety Database #	

SIX AND TWELVE MONTH
INFANT QUESTIONNAIRE

From: {Title} {First Name} {Last Name} {Company Name} {Country}	[today]
To:[reporter_first_name:corresp_contact] [reporter_last_name:corresp_contact]	

Event: Pregnancy	Product: [product_name]:[1]
AER#: [case_id]	Reply Due By: {Due Date}

Dear [reporter_first_name:corresp_contact] [reporter_last_name:corresp_contact],

Thank you for reporting your [patient_initials] pregnancy while on [product_name:first_suspect] ([generic_name:first_suspect]) therapy. Please send the completed questionnaire with requested information to the address, email or fax below.

Kindly note the following attachments:

- **SIX AND TWELVE MONTH INFANT QUESTIONNAIRE**

Respectfully Yours,

{Title} {First Name} {Last Name}
{Company Name} {Country}
Email: {email}
Fax: {fax}
Phone: {phone}

SIX AND TWELVE MONTH INFANT QUESTIONNAIRE

Mother Safety Database #

Infant Safety Database #

You may return completed form to Amgen Office Fax or Email:

Section 1 – Reporter Information

Reporter: Mother Father Health Care Professional (HCP) Other _____

Section 2 – Infant Healthcare Provider (HCP) Information

May Amgen contact the HCP for medical information regarding your child? Yes No

If yes, please provide contact information:

Name _____ Phone () _____ Fax () _____

Email _____ Address _____ City _____

State/Province _____ Zip/Postal Code _____ Country _____

Section 3 – Infant Medical Health Information

List any other medications/drugs (include vitamins and over-the-counter medications taken by the child)

Medications/Drugs	Dose	Route (e.g. oral, subcutaneous)	Frequency (e.g. daily, weekly)	Date Drug Started (dd/mm/yy)	Date Drug Stopped (dd/mm/yy)	Indication for Treatment

Has the infant had any abnormal screening tests? Yes No If yes, please explain:

Has the infant followed growth curves and developmental milestones as expected for chronological age?

Yes No If no, please explain:

Has the infant had any illnesses or persistent health problems? Yes No If yes, please explain:

Section 4 – Reporter Signature

Signature of person completing questionnaire: _____ Date: _____

Please print name: _____ Title and specialty if HCP _____

Approval Signatures

Document Name: Protocol-Published Original Evolocumab 20200408

Document Description:

Document Number: CLIN-000272100

Approval Date: 16 Jul 2021

Type of Study Protocol: Original

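### Section 8.3.2 puts major defects found in the first year into the primary analysis, but no proportion planned in the analysis section reports them

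*Protocol*

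**What the plan says.** Three places tie congenital anomalies to birth and pool them with other newborn events.

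- The endpoint table in the abstract (Section 4) lists "Number of cases reporting adverse events including complications, medical problems or congenital anomalies at birth".
- The data analysis paragraph of the abstract says "The proportion at birth with adverse events including complications, medical problems or congenital anomalies will be estimated in infants".
- Section 8.7.2.3.3 says "The proportion of infants with adverse events including complications, medical problems or congenital anomalies at birth will be assessed", with a 95% confidence interval. For later infancy it adds only "The proportion of infants with adverse events at 6 months and 12 months of age will be assessed".

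Section 8.3.2 assigns the birth item to one form: "congenital anomalies at birth will be assessed with a Post Due Date Questionnaire". That form (Appendix D) is sent 6 to 8 weeks after the due date. The same section then separates major from minor defects, requires physician adjudication of reported major malformations and classification by CDC criteria, and states: "Major birth defects identified up to 1 year of age by the mother or the healthcare provider will be included in the primary analysis".

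The limitations text in Section 8.7.5.1.1 takes a defect frequency as given ("the calculation of frequency of birth defects excludes fetal losses", where no defect was detected). It says that defects reported among losses are to be considered apart from the primary analysis.

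**The concern.** Section 8.3.2 describes a specific, adjudicated outcome and calls it part of the primary analysis. The section that sets out the primary analysis contains no proportion with that content. The one anomaly-related proportion it does contain differs in window, severity and composition.

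The study answers an FDA requirement to evaluate fetal and infant outcomes through the first year of life, and major defects are a central outcome for that purpose. Two analysts working from the same reports could give different answers. One would follow Section 8.7.2.3.3 and report the at-birth composite. The other would follow Section 8.3.2 and report major defects to 1 year. Annual reports are planned from 2022 to 2025, with a final report in 2026 (Section 12), so the choice could also change from one report to the next.

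**Working it through.** The protocol states no defect rate, expected number or sample size for this outcome, so there is no figure to reproduce. The check is a comparison of texts and one line of algebra.

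**Side by side**

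| Feature | Section 8.3.2, major defects | Section 8.7.2.3.3, at-birth proportion | Section 8.7.2.3.3, 6- and 12-month proportions |
|---|---|---|---|
| Window | up to 1 year of age | at birth | 6 and 12 months |
| Severity | major only | any anomaly | any adverse event |
| Composition | defects alone | anomalies pooled with complications and medical problems | all infant events pooled |
| Classification | adjudication, CDC criteria | none stated | none stated |
| Form | mother or provider report, medical records | Appendix D | Appendix E |

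No column of Section 8.7.2.3.3 matches the Section 8.3.2 column.

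**Where a late-found defect goes.** Take a major defect first recognised at 10 months. It falls after the Appendix D form, so it is outside the at-birth proportion. It can be reported on the Appendix E form, which has no birth-defect item. The form asks about screening tests, growth and milestones, and a general health question: "Has the infant had any illnesses or persistent health problems". If reported there, the defect counts as one adverse event among all others and can appear in a line listing. It enters no proportion of anomalies or of major defects.

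**Size of the gap**

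- p = proportion of infants with a major defect identified by 1 year (not given).
- f = share of those defects first identified after the birth report (not given).
- Major defects held in the at-birth proportion: p(1 − f).
- Relative shortfall against Section 8.3.2: [p − p(1 − f)] / p = f.

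| Assumed f | Fraction of Section 8.3.2 defects held at birth, 1 − f |
|---|---|
| 10% | 90% |
| 30% | 70% |
| 50% | 50% |

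The relative shortfall depends neither on p nor on the number of reports, so more reports do not reduce it. It applies to the major-defect content of the at-birth proportion. The composite as a whole also counts minor anomalies and every other newborn problem, so its total may lie well above p and cannot be read as a defect proportion in either direction.

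**Denominator.** Section 8.7.2.3.3 sets the general denominator as pregnant exposed women but phrases the birth item as a proportion of infants. Section 8.7.5.1.1 keeps losses without a detected defect out of the defect frequency, and treats defects found in losses apart from the primary analysis. Appendix D allows for multiple births. A first-year defect proportion therefore needs its own stated denominator.

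**The case against.** **These are two outcomes, not one defined twice.** The at-birth composite summarises all newborn events, and Section 8.3.2 describes major defects with their own rules. This is a fair reading, and the fix keeps both. What remains is that the second outcome is assigned to the primary analysis and then not stated there. The layout of a table may be left to an analysis plan, but the protocol itself should say consistently what its primary analysis counts.

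**An anomaly is by nature present at birth**, so the birth wording may describe the condition and the 1-year wording the period of detection. This cannot be excluded. Against it, Section 8.3.2 ties the birth item to the Post Due Date Questionnaire and lists the 6- and 12-month outcomes separately with another form. Even on this reading, the differences in severity and composition remain.

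**Late-found defects are still reported.** This stands. A reader might infer that such defects are dropped from the study, or that no defect frequency was intended. The documents support neither inference: the 6- and 12-month proportions and the line listings can hold these cases, and Section 8.7.5.1.1 presupposes a defect frequency. The gap is in the stated proportions, not in all reporting.

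**Conclusion.** The mismatch is real and worth correcting. Sections 8.3.2 and 8.7.5.1.1 presuppose a primary birth-defect frequency that the endpoint table, the abstract and Section 8.7.2.3.3 never state. The at-birth proportion that they do state omits, from its major-defect content, the share of defects identified late.

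That share is not in the protocol, so the size is known only as a relationship: the shortfall equals f, and the values of 10% to 50% are illustrations. A reader might want to go further and express the shift in percentage points or standard errors. That would need an assumed defect prevalence and an assumed number of infants. The protocol gives neither, and Section 8.5 leaves study size to the number of reports received. Confidence is high in the textual mismatch; its numerical effect is open.

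**What to change.** Make the same change in the endpoint table, the data analysis paragraph of the abstract and Section 8.7.2.3.3:

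1. Add a separate primary proportion, with 95% confidence interval, of live-born infants with a major birth defect identified from birth to 12 months, adjudicated and classified as in Section 8.3.2.
2. Use live-born infants with known outcome as the denominator, not pregnant women, and report beside it how many have 12-month follow-up.
3. Show defects in fetal losses separately, as Section 8.7.5.1.1 already says.
4. Keep the at-birth composite as a separate summary of all newborn events.

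The cost is wording in three places, one more table row, and an amendment that needs FDA review and agreement under Section 11.1. No new form is strictly required, because Section 8.3.2 already accepts reports from the mother, family or provider and the use of medical records. One weakness remains: Appendix E has no birth-defect item and Section 8.7.7 expects loss to follow-up, so the new proportion may be too low where 12-month follow-up is incomplete. Reporting the number followed to 12 months makes that visible.
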